9.3 INVESTIGATOR APPROVAL

It is the responsibility of the investigator to obtain prospective approval of the study protocol, protocol amendments or changes, informed consent forms and other relevant documents (e.g., advertisements) from the IRB. All correspondence with the IRB should be retained at the site. Copies of IRB submissions and approvals should be forwarded to AMO. Study sites will obtain IRB approvals and fulfill any other site-specific requirements. The investigator is required to report to AMO within five working days any withdrawal of approval by the reviewing IRB for his/her participation in the investigation.

Prior to the start of subject enrollment, the following documents must be signed and returned to AMO:

- Confidentiality Agreement
- Clinical Trial Agreement
- Investigator Agreement/Protocol Signature page
- Clinical Investigator Brochure Signature page
- Financial Disclosure form
- Signed and dated copy of investigator's current curriculum vitae
- Copy of the investigator's current medical license
- Hospital/Ambulatory Surgery Center Clinical Study Acknowledgement, if required

By signing the study documents, the investigator agrees to conduct this study according to the obligations above and all other applicable regulatory and legal requirements.

10. EXPERIMENTAL PLAN

10.1 OVERVIEW

This study will be conducted in accordance with U.S. Code of Federal Regulations, the Declaration of Helsinki, ISO 14155 and all other applicable laws and regulations. The study will not begin until regulatory and IRB approvals have been obtained.

This study will be a prospective, multicenter, paired-eye, randomized, and masked clinical investigation conducted at up to 10 sites. Up to 241 subjects will be enrolled to achieve approximately 230 randomized and contralaterally-operated subjects to ensure approximately 200 evaluable subjects at 3 months. After informed consent is obtained and confirmation that all inclusion/exclusion criteria are met, the eye(s) may be randomized.

After signing the informed consent, subjects meeting all inclusion and exclusion criteria will be randomly assigned in a 1:1 ratio to receive either the bacterially-derived Healon5 or the animal-derived Healon5 control for the first-eye surgery and the other study product for the second-eye surgery. Prior to randomization for each subject, the investigator will choose which eye to operate on first based on his/her standard clinical practice (e.g., the eye with the worse cataract, poorer best corrected distance vision and/or more severe optical/visual complaints). All subjects are intended to have bilateral cataract surgery with the second-eye surgery occurring after the 1-week postoperative exam for the first eye, but no more than 45 days after the first-eye surgery. All subjects will be examined through 3 months postoperatively according to the visit schedule described in Section 10.2, Visit Schedule.

An independent Data Safety Monitoring Board (DSMB) will monitor complications and adverse events that occur during the study.

Key data collection for all subjects includes IOP, ECC, manifest refraction, visual acuities, biomicroscopic slit-lamp findings, complications and adverse events. A chart summary of all examination procedures required at each study visit is provided in **Appendix A**. If needed, specific equipment necessary to perform the required procedures will be supplied for the duration of the study (**Appendix B**).

10.2 VISIT SCHEDULE

The study visit schedule for all study subjects is outlined in **Table 1**.

All subjects enrolled are intended to have bilateral cataract surgery with the second-eye surgery occurring 14-45 days after the first-eye surgery (and after the 1 week exam for the first eye). After each surgery, each eye will be examined at 6 hours (4-8 hours) postoperatively, 1 day (20-28 hours) and again at 1 week (7-14 days). Additionally, following the second-eye surgery, both eyes will be evaluated at 1 month (23-37 days) and 3 months (75-105 days). Unscheduled visits may be conducted as necessary at the discretion of the investigator for medically-indicated follow-up.

TABLE 1: Visit Schedule

VISIT	EYES EVALUATED	EXAM	VISIT WINDOW
1	Both Eyes	Preoperative Exam	Within 45 days prior to 1 st surgery
2	First Eye	Operative	0-45 days after preoperative exam
3	First Eye	6 hours	4-8 hours postoperative
4	First Eye	1 day	20-28 hours postoperative
5	First Eye	1 week ^a	7-14 days postoperative
6	Second Eye	Operative ^a	14-45 days after 1 st eye surgery
7	Second Eye	6 hours	4-8 hours postoperative
8	Second Eye	1 day	20-28 hours postoperative
9	Second Eye	1 week	7-14 days postoperative
10	Both Eyes	1 month	23-37 days postoperative from 2 nd implant
11	Both Eyes	3 months	75-105 days postoperative from 2 nd implant

^a The 1-week exam for the first eye must be completed prior to surgery on the second eye.

10.3 PREOPERATIVE PROCEDURES

All subjects enrolled in the study must sign the current IRB-approved informed consent document and meet the inclusion/exclusion criteria. The informed consent must be signed before any study-specific examinations are performed, and this must be documented in the source documents. An Authorization for Use/Disclosure of Health Information Form (HIPAA authorization) must also be signed.

All preoperative testing for the study must be completed within 45 days prior to the first surgery. Data from routine (non-study-specific) preoperative cataract examinations performed prior to the informed consent process may be included, provided these tests are conducted no more than 45 days prior to the first-eye surgery. If a test/exam is required by the protocol, but is not part of routine testing the investigator performs for cataract evaluations, that test/exam is considered to be study-specific and is not to be done until after the informed consent has been signed by the subject. Following the informed consent process, completion of the preoperative study exam, determination that the subject meets all of the required entrance criteria and determination of the first eye to be operated on, the subject may be randomized and scheduled for surgery.

As the Informed Consent Form is signed at the beginning of the preoperative study exam, some subjects may not qualify after study-specific testing is performed. Subjects will be considered screen-failures if they do not qualify or if they qualify but decide not to proceed with surgery. These subjects will be exited from the study.

Preoperative testing to be performed for each eye includes the following:

POTENTIAL DISTANCE VISUAL ACUITY

The subject must be capable of achieving Snellen 20/40 or better best corrected distance vision in each eye after cataract extraction and IOL implantation. The surgeon may use his/her judgment, the Potential Acuity Meter (PAM), or other methods (e.g., pinhole, laser interferometer, etc.) to estimate the subject's potential postoperative acuity.

INTRAOCULAR PRESSURE (IOP)

Preoperative IOP cannot be ≥ 20 mmHg. Additionally, medically-controlled ocular hypertension and/or glaucomatous changes in the optic nerve are exclusionary.

ENDOTHELIAL CELL COUNT (ECC)

Subject must have an ECC of at least 1800 cells/mm² to be enrolled. Three separate images will be taken of each eye and the lowest value of the three counts, as calculated by the Konan Specular Microscope, will be recorded. Note that ECC inclusion/exclusion criteria will be determined by the site; however, ECC images will be additionally analyzed by a centralized reading center for study endpoint analyses. Further instructions are provided in **Appendix C**.

ADDITIONAL PREOPERATIVE INFORMATION TO BE COLLECTED:

- Informed consent documentation
- Subject demographic information
- Determination of the first eye to be operated on and planned surgery dates for each eye
- Ocular history, including presence of ocular pathology for each eye
- Snellen BCDVA for each eye
- Ocular and systemic medications

10.4 RANDOMIZATION AND MASKING

A randomization list will be created by the AMO biostatistician for each investigative site. Subjects will be randomly assigned to receive either the bacterially-derived Healon5 or the animal-derived Healon5 control in the first operative eye on a 1:1 basis; subjects will then receive the OVD not used in the first-eye surgery in the fellow eye. The randomization codes will be uploaded into the electronic data capture system (EDC). Study personnel at the site will be trained in the randomization process through the EDC system and will randomize subjects as they are enrolled. Randomization will take place after the subject has signed the informed consent document, has met all inclusion and exclusion criteria, and the investigator has documented which eye will be the first to undergo surgery.

As part of the informed consent process, the investigator or delegate will explain to the subject the requirements of a randomized, masked study and the differences between the two OVDs.

In order to ensure masking of all study personnel, both the investigational and control OVDs will be packaged the same in white boxes labeled "Investigational Device".

10.5 STUDY MEDICATIONS AND IOP MANAGEMENT

Medications should be used as indicated below to minimize variation in treatment. Each investigator must be consistent with his/her medication regimen for each eye enrolled in the study. All preoperative, intraoperative, and postoperative medications must be recorded on the subject source documents. Routine use of intraocular anti-hypertensive medication and miotics is not permitted.

3 Days Preoperative:

Standard medication regimen, however:

- No steroids
- Ketorolac tromethamine (0.45% or 0.5%) 1 gtt bid

Operative:

Standard intraoperative regimen, **however:**

- No steroids
- At completion of case, topical antibiotic, anti-inflammatory and steroid permissible
- **No routine injection of antibiotics and/or steroids at close of procedure**

Postoperative:

- Prednisolone acetate and ketorolac tromethamine (0.45% or 0.5%):
 - 1gtt each qid x 1 week (first week postop)
 - 1gtt each tid x 1 week (second week postop)
 - 1gtt each bid x 1 week (third week postop)
 - 1gtt each qd x 1 week (fourth week postop)
- NO IOP-reducing medications are to be given, and no IOP-reducing interventions are to be done unless IOP is ≥ 30 mm Hg
- Other medications, aside from IOP-reducing medications and anti-inflammatories, may be given per the investigator's standard medication regimen

IOP Management: (at any postoperative visit)

IOP < 30 mm Hg: No treatment

IOP \geq 30 mm Hg: (Complete an SAE/ADE Detailed Page; Section 11)

- IOP-reducing medications are to be administered per the investigator's standard of care

The administration, at any time, of IOP-reducing drugs shall be documented, and the data from those subjects will be analyzed separately. If a subject's IOP remains elevated at 30 mm Hg or greater for longer than 24 hours, additional measurements must be made every 24 hours until the IOP returns below 30 mmHg.

10.6 OPERATIVE PROCEDURES

Both the investigational and the control OVDs should be generally used as the investigator would use his/her standard OVD(s) during the cataract removal and lens implantation procedure. At a minimum, the viscoelastic should be used to inflate the anterior chamber and coat the endothelium prior to cataract extraction and for IOL insertion. All investigators are to completely remove the OVD prior to the completion of each case using irrigation/aspiration (I/A). All subjects must be implanted with either a TECNIS 1-Piece Monofocal IOL (Model ZCB00 or PCB00), TECNIS 1-Piece Multifocal IOL (Model ZKB00, ZLB00 or ZMB00), or the TECNIS Symphony Extended Range of Vision IOL (Model ZXR00) for this study. Lenses should be inserted into the capsular bag using the UNFOLDER Platinum 1 Series Implantation System (DK7796 handpiece with the UNFOLDER Platinum 1 Series cartridge, Model 1MTEC30) or the ONE SERIES Ultra Implantation System (DK7786 or DK7791 handpiece with the One Series Ultra cartridge).

Standardization of surgical technique across all study sites is important in reducing outcome variability. Therefore, all sites are to adhere to the following technique unless operative complications require otherwise.

- Operative medications in accordance with Section 10.5
- Investigator's routine, small-incision, cataract extraction
- Laser assisted cataract surgery and AK or LRI will be allowed bilaterally.
- Implantation of TECNIS IOL Models ZCB00, PCB00, ZKB00, ZLB00, ZMB00 or ZXR00
- Optic/haptics placed in capsular bag
- Sutureless incision closure

Operative case report forms will include the following information:

LENS REMOVAL

Lens removal may occur using phacoemulsification only or through laser fragmentation and phacoemulsification/aspiration.

SURGICAL COMPLICATIONS

Should a surgical complication occur in either the first or second eye, implantation of a study lens will be at the investigator's discretion. However, in the event of capsular bag or zonular rupture, the TECNIS IOL should not be implanted if the complication may result in lens instability. Additionally, the lens is not to be implanted in the sulcus. In this case, the investigator may implant his/her choice of a back-up, non-investigational IOL. The subject will be followed per the protocol, although data may be analyzed separately.

MEDICATIONS

Medications not to be used preoperatively and intraoperatively are detailed in Section 10.5, Study Medications and IOP Management. All efforts should be made to follow the regimen described. Any changes or additions to the medications used will be considered a protocol deviation.

ADDITIONAL OPERATIVE INFORMATION TO BE COLLECTED INCLUDES:

- Date of surgery
- Operative eye
- Lens model, power and serial number
- Other surgical procedures
- Surgical technique according to protocol

10.7 POSTOPERATIVE PROCEDURES

Postoperatively, subjects will be examined according to the schedule in Section 10.2, Visit Schedule. Only the most recently operated eye will be evaluated at the 6-hour, 1-day and 1-week visits. Both eyes will be evaluated at the 1-month and 3-month visits.

To maintain consistency throughout the study, it is recommended that a single individual (study technician or coordinator designated by the investigator) conduct all postoperative study-related testing. In addition, a back-up person should also be designated and trained. The biomicroscopic slit-lamp exam, however, should be performed by the investigator or other qualified designee.

Note: Subjects are not to wear contact lenses postoperatively until after completion of this study. Wearing contact lenses may potentially cause corneal edema or topography changes that may influence the visual acuity results. During the study, if correction is required, spectacles should be prescribed.

The postoperative case report form will include the following information, although not all are required at every visit (See **Appendix A**):

DISTANCE VISUAL ACUITY TESTING

Snellen monocular UCDVA and BCDVA will be measured for all subjects postoperatively under photopic lighting conditions. For eyes unable to achieve a postoperative BCDVA of Snellen 20/40, a reason must be specified.

IOP

IOP will be measured at each postoperative visit by Goldmann applanation. Any IOP measurements of 30 mmHg or greater are to be considered a “spike”. An SAE/ADE Detailed Page must be completed; spikes are to be managed as described in Section 10.5, Study Medications and IOP Management.

ECC

All endothelial cell counts will be performed with a Konan non-contact specular microscope preoperatively and at three months postoperatively. Three photos will be taken at each exam and electronic or paper copies sent to AMO. Further instructions are provided in **Appendix C**.

BIOMICROSCOPIC SLIT-LAMP EXAM

A biomicroscopic slit-lamp exam must be performed at each postoperative visit to determine the presence or absence of any medical or lens findings, complications or adverse events.

Findings of aqueous cells and flare, corneal edema, synechia and fibrin are to be rated using standardized grading scales of 0 to +4 (0 = none, +4 = severe) during the slit-lamp biomicroscopy. The specific grading scales are provided in **Appendix D**.

DILATED FUNDUS EXAM

A dilated fundus exam is to be performed only if medically indicated.

OCULAR SYMPTOMS (NON-DIRECTED; SPONTANEOUS)

Subjective ocular symptoms are to be assessed at each postoperative visit by asking “Are you having any difficulties with your eyes/vision?” Subjects should not be prompted for specific responses; however, if a subject reports halos, night glare or starbursts, the level of severity should be determined (mild, moderate or severe).

MEDICATIONS

Postoperative medications should be used as described in Section 10.5, Study Medications and IOP Management. Every attempt should be made to adhere to the regimen. Any changes or additions to the medications prescribed will be considered a protocol deviation. Medications will be recorded on each postoperative case report form as applicable.

ADVERSE EVENTS

Subjects should be assessed at each visit for occurrence of and/or change in status of any adverse events, particularly serious and/or device-related adverse events. See Section 11.0, Adverse Events, and **Appendix E**, Adverse Event Reporting Instructions, for further information.

10.8 EXIT OF SUBJECTS

An Exit Case Report Form will be submitted for all subjects, either when they complete the study or if they exit early.

It is the responsibility of the investigator to provide complete follow-up data to AMO for each subject, and every attempt should be made to gather that complete follow-up data for all subjects enrolled as missing data can have a negative effect on the study results. Patients who would be traveling, relocating or otherwise unavailable for postoperative follow-up visits should not be chosen for this clinical study.

If a subject dies prior to study completion, he/she will be documented as discontinued from the study along with the reason for death. Subjects will be considered “lost-to-follow-up” from the study only if irretrievably lost for unavoidable reasons such as: subject moved/unable to locate, subject uncooperative/refuses further study participation, subject ill/unable to travel. In the event of subject relocation, efforts must be made by the investigator to secure follow-up information (i.e., IOP, slit-lamp findings and general visual acuity, etc.) from the subject’s new physician.

A subject will be considered a non-randomized screen failure if he/she does not meet the inclusion/exclusion criteria or if consent is withdrawn prior to randomization.

A subject will be considered a randomized screen failure if the subject is randomized but does not undergo surgery or receive one of the study OVDs for various reasons including: the surgery being aborted, the subject withdrawing consent prior to treatment or the subject dying prior to treatment. If a subject receives the study OVDs in either eye, he/she is to be followed according to the protocol.

If a subject is exited early from the study, the investigator will submit an Exit Case Report Form indicating the reason for study exit. In the event of a serious adverse event, the subject may be exited from the study; however, efforts must be made by the investigator to follow the subject until resolution of the adverse event.

Following study completion or early exit, subjects will be informed about which OVD was used in each eye. Additionally, all study subjects are to be instructed to undergo regular eye examinations at least yearly and to return to their doctor if any eye complications are experienced in the interim.

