11. ADVERSE EVENTS AND PRODUCT COMPLAINTS

11.1 ADVERSE EVENT DEFINITIONS

Adverse Event (AE)

An adverse event is defined (following ISO 14155) as any untoward medical occurrence, unintended disease or injury, or untoward clinical signs (including abnormal laboratory findings) in subjects, users or other persons, whether or not related to the study device.

Serious Adverse Event (SAE)

An adverse event is considered serious (following ISO 14155) if it is an untoward occurrence which may or may not be related to use of the study device that

- is sight- or life-threatening,
- results in death,
- requires inpatient hospitalization or prolongation of hospitalization (a planned hospitalization for a pre-existing condition without a serious deterioration in health is not considered a serious adverse event),
- results in permanent impairment of a body structure or body function,
- necessitates medical or surgical intervention to prevent permanent impairment to a body structure or function, or
- results in fetal distress, fetal death or a congenital abnormality or birth defect

Device-Related Adverse Event/Adverse Device Effect (ADE)

A device-related adverse event is defined as any adverse event that is believed to be definitely, probably or possibly related to the study device (following the guidelines in Section 11.4, Causal Relationship). A device-related event is also considered an adverse device effect (ADE; following ISO 14155) resulting from the use of the study device that may result from user error, insufficiencies or inadequacies in the instructions for use, deployment, implantation, installation, operation or any malfunction of the device.

Study-Specific Serious Anticipated Adverse Events

The following is a list including, but not limited to, ocular adverse events that are anticipated and must be reported to AMO for this study. Any events that are unlikely but anticipated (i.e., endophthalmitis) will be reported to the FDA.

- Endophthalmitis/Intraocular infection
- Hypopyon
- Hyphema
- IOL dislocation
- IOP 30 mmHg or greater at any time or persistent IOP of any level requiring treatment
- Cystoid macular edema
- Pupillary block
- Retinal detachment/tear
- Persistent corneal edema
- Persistent iritis
- Visual symptoms requiring secondary surgical intervention (e.g., lens removal)
- Tilt and decentration requiring secondary surgical intervention (e.g., repositioning)
- Residual refractive error resulting in a secondary surgical intervention

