11.5 ADVERSE EVENT FOLLOW-UP

For every adverse event, appropriate measures should be undertaken to treat and/or monitor the subject until resolution occurs. Obtain and maintain in the subject's files all pertinent medical data relating to the event including the subject's medical records and medical reports and/or judgments from colleagues or outside specialists who assisted in the treatment and follow-up of the subject. The investigator should keep AMO closely informed as to the outcome of serious and/or device-related adverse events, thereby allowing AMO to comply with the appropriate regulatory reporting requirements. A SAE/ADE Resolution Form should be submitted each time the subject returns to the investigator or other specialist(s) for follow-up of a serious and/or device-related adverse event until resolution of the event. Any subject who is exited from the study due to a serious and/or device-related adverse event will be followed until the outcome is determined.

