19. TERMINATION OF THE INVESTIGATION

The clinical investigation will be suspended in the event of high levels of complications and/or adverse events that are unexpected in nature and/or severity and evaluated as to causality relative to the study device. The clinical investigation may be suspended if the DSMB, Medical Monitor or IRB, upon review and evaluation of the clinical data, finds unacceptable clinical performance or the level of single or total complications and/or adverse events unacceptable for continuation of the investigation (such as if any subject has an IOP \geq 30 mmHg at one week postoperatively or later).

If causality is shown not to be related to the study device, the study may be resumed in accordance with the IRB and regulations of the FDA. The study will be terminated if causality is shown to be related to the study device.

Additionally, the investigator, or AMO, may stop a subject's participation at any time. AMO may also stop the study at any time for reasons it determines appropriate. However, no suspension of the study would be made to disadvantage the study subjects. Following suspension of the study for any reason, all study subjects who have already received treatment would continue to be followed through completion of the study visit schedule.

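### The protocol permits exit after a serious adverse event and lists every IOP of 30 mmHg or more as one, so meeting the primary safety endpoint can itself end a subject's data collection

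*Protocol*

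**What the plan says.** Protocol Section 10.8 (Exit of Subjects) holds both sides of the conflict. On one side: "If a subject receives the study OVDs in either eye, he/she is to be followed according to the protocol", and "every attempt should be made to gather that complete follow-up data for all subjects enrolled". On the other: "In the event of a serious adverse event, the subject may be exited from the study", after which "efforts must be made by the investigator to follow the subject until resolution of the adverse event". Section 11.5 sets a similar endpoint for follow-up: "Any subject who is exited from the study due to a serious and/or device-related adverse event will be followed until the outcome is determined". Neither end of follow-up is tied to the 3-month visit.

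Section 11.1 places "IOP 30 mmHg or greater at any time or persistent IOP of any level requiring treatment" under the heading "Study-Specific Serious Anticipated Adverse Events". Sections 10.5 and 10.7 require the SAE/ADE page for each such reading. Section 20.5 defines the primary safety event by the same 30 mmHg threshold, at any visit.

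Section 19 adds that "the investigator, or AMO, may stop a subject's participation at any time". Its promise of continued follow-up for treated subjects applies when the study is suspended, not when one subject is stopped.

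Two features of the plan decide what an exit costs. ECC is measured after surgery only at 3 months (Section 10.7, Appendix A). The ITT population requires surgery with the test OVD in one eye and the control OVD in the other (Section 20.1; SAP Section 2.1).

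**The concern.** Meeting one co-primary endpoint is a permitted reason to stop observing the subject, and so to lose the other. The loss takes two forms:

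- **Exit after a first-eye spike, before the second surgery.** The subject never has paired OVDs and is outside ITT. The planned multiple imputation does not reach this subject, who remains only in the all-randomized sensitivity analysis and in the separate reporting of single-OVD subjects in the safety population.
- **Exit after the second surgery.** The subject is in ITT, but the 3-month ECC of both eyes is missing and must be imputed for a group selected on an adverse outcome. Later by-visit IOP and inflammation data are lost outright, because those endpoints use available data only.

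In a non-inferiority trial, the first route can shrink an observed excess of spikes with the test OVD. The OVD is removed before the case ends (Section 10.6), so exit withdraws no exposure. It ends observation and, under Section 10.8, leads to the subject being told which OVD each eye received.

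**Working it through.** **Inputs.** Spike rate 30% per eye, correlation 0.5, one-sided alpha 0.025, ECC SD 305 cells, ECC margin 125 cells on a baseline of 2500 (Protocol 20.5; SAP 8). IOP margin 10 points (20.2). 230 treated and 200 evaluable, so 30 losses allowed (Synopsis). Second surgery 14 to 45 days after the first (10.2).

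**1. The plan's ECC power.** SD of the paired difference = 305 × √(2 × (1 − 0.5)) = 305. Power with 195 pairs = Φ(125 / (305/√195) − 1.96) = 99.99%. The stated figure of over 99% reproduces.

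**2. How many subjects could meet the exit condition.**
- P(both eyes spike) = 0.3² + 0.5 × 0.3 × 0.7 = 0.195.
- P(at least one eye spikes) = 0.30 + 0.30 − 0.195 = 0.405; × 230 = about 93 subjects.
- First-eye spikes: 0.30 × 230 = 69.

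Both counts are upper bounds. The 30% is cumulative over all visits, and the first eye's 1-month and 3-month visits come after the second surgery, so not all 69 spikes would precede it. A spike first seen at the 3-month visit costs no ECC, because ECC is taken at that visit.

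**3. What different exit shares would do.** The documents give no exit share, so *f* (the share of spike subjects who exit) is an assumption. Each exit is counted as losing the 3-month ECC.

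| *f* | Exits, 230 × 0.405 × *f* | Left with 3-month ECC |
|---|---|---|
| 10% | 9 | 221 |
| 25% | 23 | 207 |
| 50% | 47 | 183 |
| 100% | 93 | 137 |

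The 30-subject allowance is used up at *f* = 30/93.15 = 32% with no other losses. The SAP's trigger for a tipping-point analysis (more than 10% missing) is passed at about *f* = 0.10/0.405 = 25%, taking the 230 treated as the base.

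**4. ECC power under exit.** Starting from 200 pairs with *f* = 100%, 200 × (1 − 0.405) = 119 pairs remain. With the SD at 305/2500 = 12.2%, power = Φ(5 / (12.2/√119) − 1.96) = 99.4%.

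**5. Effect on the IOP comparison when the truth is at the margin.** Test 40%, control 30%, correlation 0.5, 200 pairs, each OVD first in half of the subjects. Here *f* is the share of first-eye spikers who exit before the second surgery and so leave ITT.
- P(both) = 0.12 + 0.5 × √(0.24 × 0.21) = 0.232. Test-only = 0.168; control-only = 0.068.
- First-eye spike rate = (0.40 + 0.30)/2 = 0.35, so the share kept is 1 − 0.35*f*.
- In a discordant pair the spiking eye is first half the time, so discordant pairs survive at 1 − *f*/2.
- ITT difference = 0.10 × (1 − *f*/2) / (1 − 0.35*f*).
- *f* = 25%: 0.10 × 0.875/0.9125 = 9.6 points, 182.5 pairs.
- *f* = 50%: 0.10 × 0.75/0.825 = 9.1 points, 165 pairs.
- Type I error = Φ((0.10 − difference)/SE − 1.96). At 25%, SE = 0.0345, giving about 3.3%. At 50%, SE = 0.0353, giving about 4.4%. With no exits it is 2.5%.

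Discordant pairs carry the difference, and they are lost faster than pairs overall (*f*/2 against 0.35*f*). The shift is therefore toward declaring non-inferiority.

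**The case against.** The strongest reply is that the protocol's spike pathway assumes subjects stay. Section 10.5 sets out treatment, repeat measurement until IOP is below 30 mmHg and separate analysis of subjects given IOP-reducing drugs, and does not mention exit. Section 10.8 asks for complete data and confines loss to follow-up to irretrievable cases. Section 15.1 adds measures to prevent missing data. Exit is permitted, not required. This stands: the documents do not show that sites would routinely exit subjects for a spike. It does not remove the permission, which contradicts the retention sentence in the same section.

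Several stronger readings are tempting but not supported:

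- **That the trial loses power for ECC.** It does not (step 4).
- **That imputation fills the gap for every exited subject.** It applies only to those operated with both OVDs.
- **That 69 subjects would spike before the second surgery.** That is a ceiling.
- **That the cumulative IOP endpoint loses the eye that spiked.** While its subject remains in the analysis, that eye is already counted, and its later readings cannot change the result. What can be lost is the fellow eye and the by-visit rates.
- **That ECC results would drift toward similarity.** An exit removes both eyes of the pair, and the documents give no basis for a direction.

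The SAP's worst-case analysis does include every randomized subject. That is a real safeguard, but it is a sensitivity analysis and not the primary test.

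**Conclusion.** The concern holds as an internal conflict that opens a route to outcome-dependent loss. Section 10.8 read with Sections 11.1, 11.5 and 19 makes the primary safety event a permitted reason for exit, with no duty to collect the 3-month ECC. At most about 93 of 230 subjects could meet the condition under the plan's own assumptions. How many would exit is unknown, so the exit shares used here are illustrations and not predictions. The IOP illustration also assumes that the stated share leaves before the second surgery and that the true difference sits at the margin. On those terms the bias is modest at 25% exit (type I error about 3.3%) and larger at 50% (about 4.4%), and it runs toward a non-inferiority claim. The matter merits a cheap correction. It is not evidence that the trial's conclusion would be wrong.

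**What to change.** Reconcile Protocol Sections 10.8, 11.1, 11.5 and 19 on data collection. State that an adverse event, including an IOP spike, or not proceeding to second-eye surgery does not by itself end scheduled data collection. Subjects who received a study OVD in either eye would remain in the scheduled visits, including the 3-month ECC in each operated eye, unless they die, withdraw consent or are lost to follow-up as Section 10.8 already defines it. That last category needs to stay, since a rule limited to death and withdrawn consent would create a new conflict. Make the Section 19 sentence on stopping a subject's participation consistent with this. Decisions on treating the eye, and on whether to operate on the second eye, are left as they are.

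The cost is a short amendment, plus continued attendance at visits already in the schedule for subjects who would otherwise have been exited.
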